15.8.1.2 Safety Monitoring Committee

Because we are using standard clinical vaccines that are clinically recommended for HIV-infected individuals, the need for a formal DSMB is not anticipated, but the protocol team will convene a safety monitoring committee (SMC) of at least three independent experts including one statistician to perform an interim safety review once the study has reached 50% accrual or after approximately one year has passed, whichever occurs first. The SMC will review study progress and data at least annually to ensure patient safety and feasibility of completing the study within the grant-funding period. After the review, the SMC will be asked to make a recommendation for study continuation, modification or conclusion. The SMC is composed of clinical trials experts and statisticians who are not investigators in the specific project and have no conflict of interest with the clinical study. Members of the SMC include Drs. [name], [name] and [name], who are all respected experts both in the care and treatment of HIV-infected patients and in the design, conduct, and analysis of clinical trials.

All members of the SMC will receive an introduction to the study trial and will have a clear understanding of how study investigators will approach early study termination for safety reasons. The Safety Monitoring Committee will review the safety and welfare of participants and confidentiality of data. The committee's responsibilities include: reviewing study protocols including plans for data safety monitoring, evaluating the progress of the intervention trial, evaluating participant risk versus benefit, performing assessments of any unexpected factors

that can affect the safety of study participants. The SMC will provide writing recommendations to the PI, who will distribute these to the study team, local IRB and the DAIDS Program Officer

15.8.1.3 Interim Efficacy Review:

A SMC will review trial data when at least 50% of subjects have completed the trial. There will be no formal interim assessment of efficacy. Safety data will be evaluated to determine if the study should continue as planned, should be modified to ensure patient safety or should be stopped.

15.8.2 Analysis Plan

All formal analyses of the data will be performed at the end of the study with no real time clinical decisions based on intermediate results. We will utilize a comprehensive AVRC Data Management System developed through our CFAR that can handle all dynamic aspects of clinical research studies including electronic case report form (eCRF) creation and editing, protocol design interfaces, online data entry and QA workflows, real-time accrual monitoring, multi-study data integration, role-based user permissions, integrated specimen processing workflows, an auditing system to track changes to both forms and data, and data visualization and export tools.

Sample and data collection from study participants will occur from study months 6-36 of the study. Unblinding of the study arms for data analysis of primary and secondary endpoints will occur around 44-48 months (after all participants have completed the entire study follow-up), and the final analysis of the trial will take place between 48 and 60 months.

Analysis of the Primary Hypothesis: We will determine whether average changes in levels of cell-associated HIV RNA in CD4+ T-cells are associated with administration of active vaccine or placebo using two-sided paired t-tests with alpha level of 0.05 for each of the two tests (influenza versus placebo and pneumococcus versus placebo).

Secondary analyses: Since subjects will receive multiple injections, we will determine if changes in cell associated HIV RNA in CD4+ T-cell levels are sustained over the weeks following vaccination using graphical and descriptive statistical methods. We will also explore the effect of the vaccines on the size of cell free and cell associated HIV RNA populations using linear mixed effects models and consider incorporating interactions with time to evaluate the change in effects of the vaccines over time.

Additional analyses are described in the Statistical Analysis Plan (SAP).

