Optional Stool Collection		X						X						X						
Optional Genital Secretion ^d		X				X	X	X				X	X	X				X	X	X
Hematology/Chemistry/Coagulation Panel		X				X	X	X				X	X	X				X	X	X
Immune responses		X	X	X	X	X	X	X	X	X	X	X	X	X	X	X	X	X	X	X
HIV-1 RNA sequencing		X	X	X	X	X	X	X	X	X	X	X	X	X	X	X	X	X	X	X
CD4+ T-cell Count		X	X	X	X	X	X	X	X	X	X	X	X	X	X	X	X	X	X	X
HIV-1 DNA sequencing		X	X	X	X	X	X	X	X	X	X	X	X	X	X	X	X	X	X	X
Archive Plasma		X	X	X	X	X	X	X	X	X	X	X	X	X	X	X	X	X	X	X

- Cycle 1 to begin within 30 days of screening visit
- ± 2 days
- Minimum 6 week washout period between cycles
- Paired blood and optional genital secretion sample will be collected **before** each injection
- Pregnancy Test will be repeated only if pregnancy is suspected.

Study Duration: 240 weeks

[figure not shown]
Study Regimen/Intervention: This is a double blind RCT of two vaccines (Pneumovax®23 and Fluarix® or Fluzone®) plus placebo (sterile saline injection). Study participants will be followed for 28 weeks after enrollment. During this 28-week period, blood samples will be collected on day 0 and five subsequent time points after each injection (days 2, 4, 7, 14 and 30). Optional genital secretion samples will be collected on day zero and on days 14 and 30 after each injection. Optional stool will be collected at day zero. Injections (vaccine or placebo) will be administered 12 weeks apart and in a random order, to minimize a possible bias due to the order of the vaccines.

NOTE: Fluarix® quadravalent vaccine is the flu vaccine of choice for this study. Fluzone® quadravalent vaccine may be substituted for Fluarix® only in the event that Fluarix® is unobtainable from the wholesaler/manufacturer.

Primary Objective: To determine the impact of Pneumococcus and Influenza vaccines on the HIV transcriptional activity in individuals who are virologically suppressed for at least 48 weeks on ART.

Primary Outcome: Average change in level of CD4+ T-cell-associated HIV RNA transcription from baseline to day 7 after each injection.

Figure 1. Study Design and sampling

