9.3. Study Arms

Each subject will take Influenza (Fluarix®, GSK or Fluzone®, Sanofi -Pasteur), Pneumococcal (Pneumovax®23, Merck), and placebo. Randomization will determine the order in which the subjects receive the injections. There are six possible study arms, one for each order in which someone can receive the injections:

Placebo, Flu, Pneumovax

Placebo, Pneumovax, Flu

Flu, Placebo, Pneumovax

Flu, Pneumovax, Placebo

Pneumovax, Placebo, Flu

Pneumovax, Flu, Placebo

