9.6. Enrollment and dropout

All participants will be enrolled in the first 36 months of the study to allow for a complete 28 weeks of observation for each subject. To decrease variability, we will only enroll individuals who have remained suppressed with no viral loads >50 copies/ml 48 weeks before enrollment. Viral loads are performed as part of recently funded 'ART NET' study in San Diego (1R01MH100974-01A1, PI [name]) every 6 months and in the Owen clinic every 3 months, and we will have access to both measures. Anticipating a 10% dropout, we will enroll 56 subjects into our RCT. We thus conservatively expect to achieve an evaluable sample size of 50 at study end.

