15.4 Sample Size Considerations

Examples of Power:

Primary Hypothesis (stated under the alternative): On average, participants will have a higher absolute increase in levels of cell-associated HIV RNA in CD4+ T-cells seven days after receiving either Pneumococcal or Influenza vaccinations, when compared to seven days after receiving placebo. We have chosen to provide estimates of power on the one sampled time point that is likely to show the largest effect, based on our literature review. All other sampled time points following vaccination will be evaluated as well, but to be conservative, we focus on and present power for one sampled time point for our primary hypothesis.

- Assumption: This is a cross-over study with 56 individuals receiving Placebo, Pneumococcus, and Influenza injections in random order (6 possible orders) with sufficient wash-out period in between (minimum 6 weeks) vaccinations. We expect that 6 individuals drop out, resulting in a fully evaluable sample size of 50 individuals. Pilot data were generated from the previous Spanish Study [1] to provide estimates of standard deviations (SD) of change in cell associated HIV RNA levels. From these data, we used a SD of 537 HIV RNA copies/ 10^6 CD4 T-cells for Influenza and 714 for Pneumococcus, and a pooled estimate of 625.
- Effect sizes: In Figure 3, we present the effect sizes that we have 80% power to observe at alpha levels of 0.05 (solid line) and 0.025 (dashed line). Since we will compare observations in the same individual, we will use a paired t-test that compares increases in cell-associated HIV RNA in CD4+ T-cells after 7 days for each of the active vaccine injections (Pneumococcus or Influenza) to 7 days after the placebo injection. For example, if the SD of the differences between active and placebo injection measures is 625 HIV RNA copies/ 10^6 CD4 T-cells, then we will have 80% power at alpha 0.05 to detect an effect size of 253 HIV RNA copies/ 10^6 CD4 T-cells absolute increase or decrease (two-sided test) in cell associated HIV RNA levels following active vaccination versus placebo, which is well-within the range observed in our preliminary data.

Example of Secondary Hypothesis (stated under the alternative): On average, participants will have a greater absolute maximum decrease in levels of total CD4+ T-cell-associated HIV DNA measured 2-30 days after receiving either Pneumococcal or Influenza vaccinations, when compared to 2-30 days after receiving placebo.

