15.5 Enrollment/Randomization/Blinding Procedures

Enrollment: A screening survey will establish inclusion and exclusion criteria. A screening CRF checklist and a screening survey will be completed by nursing staff. Written informed consent explained by trained clinical staff will occur before starting screening procedures. The baseline visit (study entry) and administration of the vaccine or vaccine-placebo intervention will be completed within 30 days of screening. A PID will be assigned to each individual screened for the study. PIDs will include a site code and three-digit extension. PIDs may not be reassigned even if the individual fails to enter the study. The PID must be included on every CRF and blood sample. The site must maintain a master list of PIDs in a central location. Study entry must be completed within 30 days after participant registration and inclusion/exclusion CRF have been completed.

Randomization: The study statistician will provide a randomization list to the pharmacist prior to study start. Subjects will be considered randomized at the time they have completed enrollment procedures and have received their initial vaccination. Subjects who do not receive any vaccination will not be considered enrolled and will be replaced and will have no follow-up evaluations performed. Subjects who withdraw after receiving the vaccine or vaccine-placebo intervention will be asked to complete the early termination visit.

Blinding: In order to achieve double blind administration of the vaccines, each drug or placebo will first be transferred to generic, non-labeled syringes before being delivered to the clinical staff who will administer the injection using aseptic techniques. This preparation (along with preparation of the sterile saline placebo) will take place in the AVRC pharmacy. Unblinding of the study arms for data analysis of primary and secondary endpoints will occur around 44-48 months (after all participants have completed the entire study follow-up).

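### The primary paired t-tests leave out cycle; adjusting for it costs almost nothing and protects power if the 7-day change drifts from cycle to cycle

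*Combined protocol and SAP*

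**What the plan says.** The Protocol Summary (section 6) explains why order is randomised: "Injections (vaccine or placebo) will be administered 12 weeks apart and in a random order, to minimize a possible bias due to the order". Section 9.3 sets out the design: "There are six possible study arms, one for each order in which someone can receive the injections".

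Section 15.8.2 then states the primary analysis in full: the 7-day changes are compared "using two-sided paired t-tests with alpha level of 0.05 for each of the two tests (influenza versus placebo and pneumococcus versus placebo"). Section 15.4 uses the same paired t-test for sample size. Neither section names cycle or sequence. The mixed models in 15.8.2 are secondary and exploratory; interactions with time are only to be considered, and cycle is not mentioned.

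Sections 12.3.2 and 15.5 say that the statistician supplies a randomisation list to the pharmacist. They do not say whether it is blocked or gives equal numbers per order.

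**The concern.** A three-period crossover usually carries a period term in its primary model, because conditions can differ between periods for reasons unrelated to treatment. Here the plain paired t-test treats all within-person differences as exchangeable, whichever cycles the two injections fell in. If the 7-day change differs systematically by cycle, two things follow. The cycle differences add to the spread of the paired differences and so to the standard error. And if the realised orders are uneven, part of the cycle effect moves into the estimated vaccine effect for that trial. Randomising the order guards against systematic bias, but the analysis does not use the known order to recover precision or to correct a chance imbalance.

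**Working it through.** **Inputs.** From section 15.4: "if the SD of the differences between active and placebo injection measures is 625 HIV RNA copies" per 10^6 CD4 T-cells; "we will have 80% power at alpha 0.05 to detect an effect size of 253 HIV RNA copies"; and dropout "resulting in a fully evaluable sample size of 50 individuals". From section 9.6: "Anticipating a 10% dropout, we will enroll 56 subjects into our RCT". From section 9.3: six orders. The drift d (copies per cycle, on the 7-day change) is not in the documents and is an assumption shown as a range.

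**Reproducing the plan's figure.** For a paired t-test with n = 50, SD 625, 49 degrees of freedom and two-sided 0.05, the noncentral t distribution gives a detectable effect of 252.6 at 80% power, and power of 80.1% at 253. The stated 253 is confirmed.

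**Which cycle effects matter.** Section 15.2.1 defines the endpoint as change from baseline, and baseline is Day 0 of each cycle (section 15.7). A shift in the level of HIV RNA between cycles therefore cancels. Only a shift in the 7-day change itself remains. (Section 15.1 words the endpoint as the day-7 level; under that wording level shifts would count too.)

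**Precision.** Write the within-person difference as vaccine effect + d × (cycle of vaccine − cycle of placebo) + error, with error SD 625. Over the six orders the cycle-number difference takes the values ±1, ±1 and ±2, with mean square (1+1+1+1+4+4)/6 = 2. The drift therefore adds 2d² to the variance, and SD = √(625² + 2d²). The adjusted column is simulated with simple randomisation to the six orders (15,000 runs per setting).

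| d | SD | Detectable effect, paired t | Power at 253, paired t | Power at 253, cycle-adjusted |
|---|---|---|---|---|
| 0 | 625.0 | 252.6 | 80.1% | 78.3% |
| 100 | 640.8 | 259.0 | 78.1% | 78.5% |
| 200 | 686.0 | 277.3 | 72.5% | 78.0% |
| 300 | 755.4 | 305.3 | 64.1% | 78.5% |

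To restore 80% with the paired t-test would take 60 evaluable participants at d = 200 and 72 at d = 300. If only one cycle is shifted, by s copies, the added variance is (2/3)s² and the loss is smaller: power is 77.5% at s = 200 and 70.1% at s = 400.

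**Cost of adjusting.** With near-equal orders the adjusted analysis has 47 degrees of freedom and a detectable effect of 252.8, against 252.6. With orders balanced only by chance and d = 0, simulated power is 78.3% against 80.3% for the paired t-test.

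**Shift given the realised orders.** The shift is d times the mean of (cycle of vaccine − cycle of placebo).
- Simple randomisation: SD = d × √(2/50) = 0.20d, with a simulated 95th percentile of 0.40d. At d = 200 these are 40 and 80 copies.
- Most even split of 50 (four orders of 8, two of 9): at most (2+1)/50 = 0.06d, or 12 copies at d = 200.

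**Type I error.** Averaged over simple randomisation, the paired t-test rejects a true null 4.8% to 5.0% of the time for d from 0 to 300.

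**The case against.** The strongest reply is that randomising the order already does its job. That stands: over repeated randomisation the paired t-test is unbiased and holds its level. A reader might infer that the primary estimate is biased by order. The documents support only a shift conditional on the realised counts.

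A reader might also infer imbalance from 56 not being divisible by six, or from the replacement of participants who receive no injection (15.5). Indivisibility alone is worth at most 0.06d. Syringes are unlabelled, so replacement gives no evident route to order-related selection. The list's method is unstated, which is not the same as unblocked.

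The power loss assumes that 625 excludes cycle variance. Section 15.4 can be read as the SD of the observed differences. On that reading the variance is already counted, 80% stands, and adjustment is only a possible gain.

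The case for a large drift is thin. A recent community influenza vaccination before cycle 1 (10.1.1.8) would mainly alter the influenza response in that cycle, which is treatment-by-cycle interaction. What was injected earlier is carryover. Season is largely separated from cycle number by enrolment spread over up to 36 months (9.6). Simple cycle terms address none of these. A drift of 300 copies per cycle is a 600-copy swing from cycle 1 to cycle 3, more than twice the 253 target. Below about 100 copies, benefit and cost roughly cancel when orders are balanced only by chance.

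Finally, 15.8.2 refers additional analyses to the SAP, so a cycle-adjusted sensitivity analysis may be planned there. That would not change the primary test, which 15.8.2 states completely.

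**Conclusion.** The point holds as a cheap improvement to the primary analysis, not as a flaw that invalidates it. Leaving out cycle costs mainly precision: little at a drift of 100 copies per cycle, about 8 points of power at 200 (80.1% to 72.5%) and 16 at 300 (80.1% to 64.1%). These figures rest on 50 evaluable participants, a true effect of 253, 625 being net of cycle effects, and an assumed linear drift for which the documents give no value. The conditional shift at 200 copies has an SD of about 40 under simple randomisation but is at most 12 with near-equal orders.

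Blocking alone would not recover the precision. With near-equal orders the estimate varies with SD about 625/√50 = 88.4, but at d = 200 the paired t-test still computes a standard error of about 686.0/√50 = 97.0. The choice favours adjustment because its worst-case cost is about two points of power, while the loss it guards against could be several times that.

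**What to change.** **Section 15.8.2.** Make the primary analysis cycle-adjusted. For each contrast, regress the within-person difference (vaccine 7-day change minus placebo 7-day change) on two cycle contrasts: indicator of vaccine in cycle 2 minus indicator of placebo in cycle 2, and the same for cycle 3. The intercept is the vaccine effect. A mixed model of the 7-day change, with treatment and cycle as fixed effects and participant as random effect, serves the same purpose. The regression has the merit of keeping a separate error SD for each vaccine, which suits the differing pilot SDs in 15.4 (537 and 714). Keep the plain paired t-test as a sensitivity analysis, and settle the choice before the unblinding planned for months 44 to 48.

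**Section 15.5.** State that the list is generated in permuted blocks over the six orders. If the list is already in use, state how it was generated.

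**Cost.** A change of wording and two degrees of freedom: the detectable effect moves from 252.6 to 252.8 with balanced orders. If orders are balanced only by chance and there is no cycle effect, about two points of power are lost. The cycle terms do not deal with carryover, calendar season or treatment-by-cycle interaction, and the text should not claim that they do.

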14.4 Treatment Failure

HIV treatment failure will be routinely tested by HIV RNA viral loads. If a participant's HIV treatment fails (two consecutive viral load measurements of >500 copies/ml) or their ART regimen is interrupted, then an early termination visit will be scheduled and the participants will be taken off study.

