14.5 Criteria for Discontinuation

- Active drug or alcohol use or dependence that, in the opinion of the investigator, would interfere with adherence to study requirements.
- The subject becomes pregnant during the course of the study.

- Failure by the subject to attend scheduled clinic visits may result in discontinuation.
- Request by the subject to withdraw from the study.
- The participant's HIV therapy fails.
- Request of the primary care provider if s/he thinks the study is no longer in the best interest of the subject.
- Clinical reasons believed life threatening by the physician.
- Subject judged by the investigator to be at significant risk of failing to comply with the provisions of the protocol as to cause harm to self or seriously interfere with the validity of the study results.

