15.2 Study Endpoints

15.2.1 Primary Endpoint

Average change in level of CD4+ T-cell-associated HIV RNA transcription from baseline to 7 days after each injection.

15.2.2 Secondary Endpoints:

1. Average change in level of CD4+ T-cell-associated HIV RNA transcription from baseline to 2, 4, 14 and 30 days after each injection.
2. Average change in levels of HIV DNA from baseline to 2, 4, 7, 14 and 30 days after each injection.
3. Determine selective vs. nonselective HIV RNA production from HIV DNA (by next generation sequencing and panmixis tests) among the five participants with the highest levels of cell associated HIV RNA following active vaccination.
4. Average change in levels of immune activation (soluble and cellular markers) from baseline to 2, 4, 7, 14 and 30 days after each injection.
5. Average change in levels of replication competent HIV DNA (by inducible RNA assay) among the five participants with the highest levels of cell associated HIV RNA following active vaccination.
6. Average change in levels of HIV specific T-cell immune response from baseline to 30 days after each injection.
7. Stimulation of HIV transcription by incidental illness, human herpesviruses replication and microbial translocation over the course of the study.
8. Possible immunomodulatory effect of microbiome composition
9. Vaccine administration will be safe for all included participants.

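### The primary paired t-tests discard a vaccine response measured before a participant leaves if placebo had not yet been given; the loss depends on randomised order and biases the estimate downward if exit follows response

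*Combined protocol and SAP*

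**What the plan says.** The primary endpoint (15.2.1) is "Average change in level of CD4+ T-cell-associated HIV RNA transcription from baseline to 7 days after each injection". Section 15.8.2 compares each vaccine with placebo "using two-sided paired t-tests with alpha level of 0.05 for each of the two tests (influenza versus placebo and pneumococcus versus placebo". Linear mixed models appear in the same section only as exploratory secondary work.

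On dropout, 9.6 states "Anticipating a 10% dropout, we will enroll 56 subjects into our RCT", and 15.4 adds "We expect that 6 individuals drop out, resulting in a fully evaluable sample size of 50 individuals". Neither section says in which cycle people are expected to leave. Section 9.3 lists six orders, two with placebo first, two with it second and two with it last. Table 1 starts the cycles at baseline, week 12 and week 24.

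Several routes lead out of the study after a first injection. For virological failure or ART interruption, 14.4 says "then an early termination visit will be scheduled and the participants will be taken off study". Section 14.5 includes "Failure by the subject to attend scheduled clinic visits may result in discontinuation", along with pregnancy, withdrawal and a request by the primary care provider. Section 11.1.8 adds prohibited medications. Section 15.5 replaces only people who were never injected; later leavers are asked to attend an early termination visit.

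The supplied text gives no primary analysis set and no rule for a participant with one or two completed cycles. Section 15.8.2 refers to a separate SAP for additional analyses, and that text is not supplied.

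**The concern.** A paired test needs four samples from each person: Day 0 and Day 7 of the vaccine cycle and of the placebo cycle, which lie 12 or 24 weeks apart. Someone who leaves in between has given a valid vaccine response that the primary analysis cannot use. Two people with the same vaccine response and the same exit time can be treated differently only because of their assigned order.

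The result is then a complete-pairs estimate. It is unbiased if leaving is unrelated to the responses already observed. If people with large vaccine responses tend to leave before placebo, their values are removed selectively and the estimated effect is pulled down, toward zero when the vaccine truly raises transcription. The two primary tests may also rest on different sets of participants.

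**Working it through.** **The plan's own figures.** Inputs from 15.4: n = 50, SD of the paired difference 625, two-sided alpha 0.05. Paired t power uses the noncentral t with 49 degrees of freedom and noncentrality δ√n/SD. Solving for 80% gives δ = 252.6, against 253 stated. At δ = 253 the noncentrality is 253 × √50 / 625 = 2.86 and power is 80.1%. Enrolment is 50 / 0.90 = 55.6, rounded up to 56, and 6/56 = 10.7%. The plan's figures reproduce. With 56 pairs, power would be 84.5%.

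**Who is lost, by position of placebo.**

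| Placebo given | Leaves after cycle 1 | Leaves after cycle 2 |
|---|---|---|
| First | In neither test (placebo only) | In one test, lost from the other |
| Second | In neither; one vaccine response discarded | In one test, lost from the other |
| Last | In neither; one vaccine response discarded | In neither; two vaccine responses discarded |

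**Pairs lost per test if 6 leave.**
- All after cycle 1: 6.
- All after cycle 2: a given vaccine–placebo pair is complete only when the other vaccine comes last (2 of 6 orders), so 6 × 4/6 = 4 are lost on average.
- Split evenly: 3 + 3 × 4/6 = 5, leaving about 51 pairs.
- All after the cycle 3 Day 7: 0.

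**Vaccine responses left without a placebo partner.** A given vaccine comes first in 2 of 6 orders, and placebo comes last in 2 of 6. Random exit after either cycle therefore strands about 6 × 2/6 = 2 responses per vaccine.

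**Effect on the estimate (simulation).** Inputs: 56 people, six orders, true effect 253, SD of the difference 625, 6 leavers. The correlation ρ between cycles is not in the documents and is assumed. The per-cycle SD is 625/√(2(1−ρ)), equal for all injections.

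| Exit mechanism | Complete-pair mean | Power | All-cycles model mean |
|---|---|---|---|
| Unrelated to response (ρ 0.2–0.7) | 252 to 254 | about 80% | 252 to 254 |
| 1 of 6 is the strongest responder (ρ 0–0.5) | 247 to 248 | 79% | – |
| 2 of 6 are the strongest (ρ 0–0.5) | 243 to 246 | 78–80% | – |
| All 6 strongest, exit after cycle 1 or 2 (ρ 0, 0.25, 0.5), variances known | 217.7, 227.5, 232.8 | 70, 73, 76% | 251.5, 255.7, 254.6 |
| Same, variances estimated by REML | 219, 226, 237 | 71–76% | 252 to 260 |
| All 6 strongest among those given a vaccine first, exit after cycle 1 (ρ 0.2, 0.5, 0.7) | 219, 226, 231 | 69, 71, 73% | 253, 253, 252 |

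For 2 of 6, (253 − 243)/253 = 4.0% and (253 − 246)/253 = 2.8%. For all 6, (253 − 217.7)/253 = 14.0% and (253 − 237)/253 = 6.3%. The listed extreme runs thus span 6 to 14%. I state about 4 to 14% so as not to overstate the lower end, which moves with ρ and with when exits fall. Against a standard error of about 88, the shift is 10/88 = 0.11 SE for 2 of 6 and at most 35/88 = 0.40 SE for all 6. Under random exit the standard errors are nearly equal, about 88 for complete pairs and 87 for all cycles.

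**Which mixed model.** Section 15.4 gives SDs of change of 537 (influenza) and 714 (pneumococcus), a variance ratio of (714/537)² = 1.77. With no effect and no dropout (placebo SD assumed 300 to 714), a common-variance model has type I error of 1.5–4.2% for influenza and 4.9–7.4% for pneumococcus; the paired tests give 4.1–6.0%. Letting the variance differ by injection (placebo SD assumed 450) gives 4.4–6.4%.

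**The case against.** The strongest reply is that the plan has already paid for the loss. It enrols 56 to keep 50 and computes power on 50. That stands: a reader might infer that the trial is underpowered, and the documents do not support it.

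A reader might also infer that all 6 expected leavers will have vaccine responses thrown away. The plan gives total dropout without timing. Some would leave after placebo only, some would stay in one test, and some might leave after the last Day 7 at no cost. Six pairs per test is an upper bound.

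A third tempting inference is that biased exit is to be expected because virological failure ends participation. The documents do not show this. The failure rule uses plasma viral load, not cell-associated RNA. Entrants have been suppressed for at least 48 weeks, the trial is double-blind, 7.1.2 describes post-vaccination rises in cell-free RNA as mostly transient with mixed evidence, and no failures are forecast. A link is possible, since viral load is measured at each visit and some cited studies saw rises, but its frequency is unknown. The case in which all 6 leavers are the strongest responders is deliberately extreme.

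Finally, a common-variance mixed model would bring its own error, given SDs of 537 and 714. That objection is right and determines the form of the fix. It does not justify leaving the paired test as the only confirmatory analysis, because a covariance that differs by injection has close to nominal error in the simulation.

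**Conclusion.** The point holds in a limited form. As written, 15.8.2 produces a complete-pairs result that drops measured vaccine responses according to randomised order. Each test loses at most 6 of 56 pairs, about 5 if exits split evenly between cycles 1 and 2. There is no power shortfall, and no bias if exit is unrelated to response. If exit depends on responses already seen, the downward bias is about 2 to 4% when 2 of 6 leavers are the strongest responders and about 4 to 14% when all 6 are.

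These sizes rest on assumed between-cycle correlations of 0 to 0.5, approximately normal changes and equal per-cycle SDs. With unequal SDs, more of the bias would fall on the more variable vaccine. It cannot be concluded that no missing-data rule exists, because the separate SAP is not supplied. What can be said is that 15.8.2 names the paired t-test as the primary analysis and gives no such rule.

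**What to change.** In 15.8.2, keep the endpoint, both contrasts and two-sided 0.05 for each. Estimate the contrasts with a REML linear mixed model on the Day 0 to Day 7 change of every completed cycle. Use fixed effects for injection and cycle, an unstructured within-participant covariance indexed by injection (not a common variance), and small-sample degrees of freedom. Include every injected participant with at least one evaluable cycle. Keep the complete-pair t-tests as a named sensitivity analysis, and report how many participants contribute one, two and three cycles, by order. Align any rule in the separate SAP with this text.

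The cost is wording, settled before unblinding. It needs no new visits, samples or participants, and mixed models are already planned for secondary work. The downside is reliance on missing-at-random, which would not fully cover exits driven by something outside the model such as plasma viral load, and a primary analysis slightly harder to explain than a t-test.
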